This study does not include any formal comparison and is purely descriptive. A common data model (CDM) will be used to create aggregated data, either by the data source or by IQVIA. This CDM will define the level of aggregation and minimum information required to enable the statistical analysis of the study objectives. The aggregated datasets will be pooled for the statistical analysis.

For the primary objective, crude IRs for 1st TE events during the follow-up period per 100 PY will be described. For the calculation of crude IRs, the denominator will be the pooled person-time of all the patients within the cohort and the numerator will be all first events occurring during the follow-up period. In addition of crude IRs, incidence proportions will also be calculated.

For the analysis of secondary objectives 1, 2, 3, 4 and 6, crude IRs per 100 PY will be calculated and for secondary objective 5, descriptive tabulations will be done for SAE and TE events.

For secondary objective 1, 2, 3 the numerators will be the number of first occurrences of any SAE, 1st TMA events and 1st serious systemic hypersensitivity reaction events during the follow-up period, respectively. The denominators for the crude IRs will be the pooled person-time. For secondary objective 4, the events will be counted for each category/stratum of relevant pre-defined risk factors of TE events, to yield crude IRs of TE per category/stratum. For analysis of secondary objective 5, characteristics of TE events, SAEs, TMA events, and serious systemic hypersensitivity reactions, including anaphylaxis (e.g., diagnosis and symptoms), will be tabulated. In addition, time to the 1st

TE events, SAE, TMA events, and serious systemic hypersensitivity reactions, including anaphylaxis events will be described by Kaplan-Meier curves. For analysis of secondary objective 6, calculation of crude IR and crude incidence proportion of TE events, SAEs, TMA events, and serious systemic hypersensitivity reactions, including anaphylaxis, will be calculated, and tabulated for FVIII prophylaxis use (yes/no) prior to emicizumab treatment.

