7.2. OBJECTIVES

The primary objective for this study is to determine the incidence of TE events.

The secondary objectives for this study are:

- 1. To determine the incidence of serious adverse events (SAEs).
- 2. To determine the incidence of thrombotic microangiopathy (TMA) events.
- 3. To determine the incidence of serious systemic hypersensitivity reactions, including anaphylaxis.
- 4. To characterise the risk profile in terms of pre-defined risk factors of TE events in the patient population.
- 5. To describe characteristics of TE events, SAEs, TMA events, and serious systemic hypersensitivity reactions, including anaphylaxis (e.g., diagnosis and symptoms).
- 6. To characterise the impact of the prior use of FVIII prophylaxis on the incidence of TE events, SAEs, TMA events, and serious systemic hypersensitivity reactions, including anaphylaxis.

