8.2.6.1. Inclusion Criteria

Patients must have met the following diagnostic criteria to be included in the study:

- Diagnosis of congenital HA.
- Moderate disease classification $(1\% \le FVIII \le 5\%)$.
- Severe bleeding phenotype, defined as the patient previously having had spontaneous bleedings and for whom prophylaxis is required to prevent such bleeding or other life-threatening complications per physicians opinion or as otherwise noted in the data source (Srivastava et al., 2020). Severe bleeding phenotype will be captured using the following criteria:
 - Ongoing or previous prophylactic treatment with clotting FVIII infusions (Carcao et al., 2020) during the 12 months prior to the index date.
 Or:
 - Spontaneous bleeding, defined as a bleeding that was not caused by trauma or a medical procedure at any time in the past prior to the index date.

Or:

• An annualised bleeding rate (ABR) of \geq 2 events/year in the 12 months prior to the index date.

Based on previous studies on bleeding phenotypes among moderate patients with haemophilia where ABR≥2 is above the 3rd ABR quartile (Kloosterman et al., 2022) or at the median and above (den Uijl et al., 2014).

Due to the variability of reporting in the data sources, the exact operational definition of the severe bleeding phenotype will vary between data sources. Table 1 shows the different criteria that can be fulfilled in each specific database.

Hemlibra—F. Hoffmann-La Roche Ltd

Protocol BO44691, Version

Data source	Country	Spontaneous bleeding prior to index date	Prophylactic treatment 12 months prior to index date	Annualised bleeding rate 12 months prior to index date
UKNHD	UK	Low	Low	Derived (number of new bleeding episodes at follow-up)
FranceCoag	France	Good	Good	Derived (bleeding events)
HemoNED	Netherlands	Captured	Captured	Derived (date/time of bleed, cause, location, and severity)
ATHN dataset	US	Not collected	Good*	Derived (bleed events)*
WBDR	Multi-country	Good	Good	Derived (total number of bleeds at baseline and at follow-up visits)
CBDR	Canada	Collected	Good	Derived (total number of bleeds)

Table 1. Applicable criteria for severe bleeding phenotype in the considered data sources.

*Bleed events not specified as traumatic or spontaneous.

UKNHD, UK National Haemophilia Database; **UK**, United Kingdom; **ATHNdataset**, American Thrombosis and Hemostasis Network; **US**; United States; **WBDR**, World Bleeding Disorders Registry; **CBDR**, Canadian Bleeding Disorders Registry.

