8.3.1. Primary and Secondary Safety Variables

The primary safety variable is TE events as recorded in the data source.

The secondary safety variables are:

- TMA
- Serious systemic hypersensitivity reactions, including anaphylaxis
- SAEs (for definition of SAEs see section 10.1.2.)

The relationship to the treatment will be detailed according to available information in each registry. If this is not available in the registry, time to the first primary or secondary safety events will be described, for further details see section 8.7.

The reporting of AEs in the considered registers for further engagement differs, an overview is given in Table 3 and the details are provided below.

Table 3.	Reporting	of adverse	events among	the considered	data sources.
			U		

Data source	Country	Coding standard
UKNHD	UK	Local adaptation of EUHASS
FranceCoag	France	EUHASS (ICD-10 used for further classification of malignant disorders)
HemoNED	Netherlands	EUHASS
ATHNdataset	US	SNOMED, MedDRA
WBDR	Multi-country	Standardised module
CBDR	Canada	CHESS

UKNHD, UK National haemophilia database; **UK**, United Kingdom; **EUHASS**, European Haemophilia Safety Surveillance; **ATHNdataset**, American Thrombosis and Hemostasis Network; **US**; United States; SNOMED **CT**, Systemized Nomenclature of Medicine – Clinical Terms; **MedDRA**, Medical Dictionary For Regulatory Activities; **WBDR**, World Bleeding Disorders Registry; **CBDR**, Canadian Bleeding Disorders Registry; **CHESS**, Canadian Hemophilia Surveillance System; **ICD**, International Classification Of Diseases.

The European Haemophila Safety Surveillance (EUHASS) system is a pharmacovigilance program that aims to monitor the safety of treatments for patients with haemophilia and other inherited bleeding disorders in Europe through a prospective AE reporting system. The program started in October 2008 and includes participating centres located across more than 30 European countries. The following events are reported to EUHASS either as they occur or as a minimum at the end of every 3-month surveillance period (European Haemophilia Safety Surveillance, n.d.):

- Acute or allergic events
- Transfusion-transmitted infections
- Inhibitors
- Thromboses
- Malignancies
- New cardiovascular events
- Neurological events
- Unexpected Poor Efficacy
- Other AE Possibly Related to Concentrate
- Deaths

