The general principles of data management and statistical analyses will be described in detail in the Data Management Plan (DMP) and SAP, respectively. Routine procedures will include checking electronic files, maintaining security and data confidentiality, following analysis plans, and performing quality control (QC) checks of all programmes. All data checks to be performed on completeness, plausibility, and consistency of collected data will be described in detail with identification of data discrepancies.

Data will be harmonised and standardised as appropriate using a CDM. Within each data source, a CDM will be used to create aggregated datasets from the collected PLD in a pre-defined standard format. This CDM defines appropriate level of aggregation and minimum information required to enable the statistical analysis of the study objectives.

For registries with only aggregated data transfer and no access to PLD by IQVIA, the CDM will be applied by the data provider to create the aggregated data from the specific data source based on data specifications provided by IQVIA. These aggregated datasets are then delivered to IQVIA who then will perform the centralised data collection and statistical analysis of the study. In such cases, only aggregated data will be transferred to IQVIA servers.

For an overview of the data sources that allow for access to PLD, please refer to Table 7.

Hemlibra—F. Hoffmann-La Roche Ltd Protocol BO44691, Version 2.0

Once at the IQVIA servers, the aggregated data originating from the data sources will be combined with the aggregated PLD analysed by IQVIA.

A brief overview of the proposed CDM workflow depicting the different stages as described above is shown in Figure 2. The workflow presented constitutes a high-level overview of the CDM process and exact details especially how this would translate to the underlying programming pipeline and output generation will be detailed in DMP and SAP.

Figure 2. A high-level overview of CDM workflow.

IQVIA will develop a DMP for the purpose of this study. DMP will be created before data collection begins and will describe in detail all data checks to be performed on completeness, plausibility, and consistency for collected data and all steps necessary from raw data to final database such as, but not limited to, database development, additional data collection process, medical coding considerations and conventions, query edition and database validation.

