8.7.2. Planned Analyses

For the analysis of the primary objective and secondary objectives 1, 2, and 3 the overall crude and crude stratified IRs will be calculated. The person-time of each patient will be based on the follow-up and censoring criteria presented in section 8.2.4. and 8.2.5.

For the calculation of crude IRs, the denominator will be the pooled person-time of all the patients within the cohort. The patient time-at-risk will be calculated from index date until the date of an incident event or censoring, whichever occurs first. All first events occurring during follow-up period will be counted in the total number of events. Crude IRs will be presented per 100 PY with 95% CI.

For the primary objective, the numerator will be the number of first TE events of all patients within the cohort. For secondary objectives 1, 2, 3 the numerator will be the number of first occurrences of any SAE; TMA events or serious systemic hypersensitivity reactions, including anaphylaxis; respectively.

For the analysis of secondary objective 4, calculation of crude stratified IRs of 1st TE events will be done. The events will be counted for each category/stratum of relevant pre-defined risk factors (see section 8.3.2.4. for a listing of considered risk factors). More details on the risk factor based tabulations will be presented in SAP.

For analysis of secondary objective 5, characteristics of TE events, SAEs, TMA, and serious systemic hypersensitivity reactions, including anaphylaxis (e.g., diagnosis and symptoms), will be tabulated. In addition, time to 1st TE event; time to 1st TMA event; time to 1st serious systemic hypersensitivity reactions, including anaphylaxis; and time to any 1st SAE event will be described by Kaplan-Meier curves.

For analysis of secondary objective 6, calculation of crude IR and crude incidence proportion of TE, TMA events, SAEs and serious systemic hypersensitivity reactions, **Hemlibra—F. Hoffmann-La Roche Ltd** Protocol BO44691, Version 2.0

including anaphylaxis, will be calculated and tabulated for FVIII prophylaxis use (yes/no) prior to emicizumab treatment.

Patient demographic and clinical characteristics will also be tabulated in relation to the AEs (TE events, SAEs, TMA events and serious systemic hypersensitivity reactions, including anaphylaxis) and in total.

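### Objective 6 seeks the impact of prior FVIII prophylaxis from crude rates pooled over registries that differ in SAE capture and in prophylaxis recording, so the SAE contrast is open to confounding by registry

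*Protocol*

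**What the plan says.** **Aim.** Objective 6 (Protocol 7.2) is "To characterise the impact of the prior use of FVIII prophylaxis on the incidence of TE events, SAEs, TMA events" and serious systemic hypersensitivity reactions.

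**Analysis.** Section 8.7.2 fixes for it the "calculation of crude IR and crude incidence proportion of TE, TMA events, SAEs and serious systemic hypersensitivity reactions", which, "including anaphylaxis, will be calculated and tabulated for FVIII prophylaxis use (yes/no) prior to emicizumab treatment". For crude rates generally, "the denominator will be the pooled person-time of all the patients within the cohort". The synopsis says "The aggregated datasets will be pooled for the statistical analysis", and section 8.6 says that "the aggregated data originating from the data sources will be combined with the aggregated PLD analysed by IQVIA". No registry stratum, standardisation or by-registry table is named for objective 6.

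**Registry differences.** Section 8.3.1 states: "The reporting of AEs in the considered registers for further engagement differs". Section 8.2.6.1 states that "the exact operational definition of the severe bleeding phenotype will vary between data sources". Section 8.9.1 accepts that this can produce selection bias.

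**Limits the protocol sets itself.** Section 8.7.1 calls the study descriptive and rules out formal comparison of the prophylaxis groups. Section 8.7.3 offers subgroups for all objectives, including broad region, subject to patient numbers. Section 8.7.5 reports missing values separately in descriptive tables.

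**The concern.** A crude contrast of two groups is distorted by registry when two things hold together: the groups have different registry mixes, and the registries record the outcome to different degrees. The protocol gives grounds to expect both.

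- **Outcome capture.** The SAE endpoint is any SAE under the full definition in 10.1.2. EUHASS works from a list of event categories whose residual item is limited to events possibly related to concentrate, and CHESS (CBDR) follows the same method. The WBDR module has an open category for other events, and ATHNdataset codes in SNOMED and MedDRA. A category-list source can miss SAEs that WBDR can hold.
- **Group mix.** Prior prophylaxis is itself one of three routes to eligibility. Table 1 rates its recording Low in UKNHD and Good in FranceCoag, ATHNdataset, WBDR and CBDR; HemoNED's completeness is undisclosed. The other routes also vary, for example spontaneous bleeding is not collected in ATHNdataset.

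At stake is the reading of the objective 6 table. Two SAE rates printed side by side under an aim worded as impact could differ with no difference inside any registry, and nothing in the stated analysis would reveal it.

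**Working it through.** **The plan's own figure.** No figure is stated for objective 6. The one precision figure (8.5.2) is the 88% for TE events, and it reproduces. 200 patients × 4 years = 800 PY; 800 × 0.15/100 = 1.2 expected events. The upper 95% limit stays at or below 1 per 100 PY with up to 2 events, and the exact binomial probability of 2 or fewer is 88.0%. About 1.2 TE events cannot be read by subgroup, so the point bears on SAEs. The protocol gives no TMA rate; I assume TMA is no more frequent than TE.

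**Inputs from the protocol (Table 7, moderate HA patients).** UKNHD 836, FranceCoag 940, HemoNED 230, ATHNdataset 15, WBDR 2987, CBDR 299; total 5307. By reporting system (Table 3 and 8.3.1): EUHASS or CHESS type 836 + 940 + 230 + 299 = 2305 (43.4%); WBDR and ATHNdataset 3002 (56.6%).

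**Assumptions, because the protocol gives none of these.** Emicizumab starters and person-time are spread as the Table 7 counts. The true SAE rate is the same everywhere and prior prophylaxis has no effect. EUHASS/CHESS-type sources record a fraction f of what WBDR and ATHNdataset record. The share of *yes* patients in registry r is s_r.

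**Formula.** With n_r patients and capture c_r (f or 1):

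- relative rate, *yes* = Σ n_r s_r c_r / Σ n_r s_r
- relative rate, *no* = Σ n_r (1 − s_r) c_r / Σ n_r (1 − s_r)
- crude ratio = the first divided by the second

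**One case in full.** f = 0.5; s = 0.35 in UKNHD, 0.40 in FranceCoag, HemoNED and CBDR, 0.80 in WBDR and ATHNdataset.

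- *Yes*: 2841.7 / 3281.8 = 0.866
- *No*: 1312.8 / 2025.2 = 0.648
- Ratio: 0.866 / 0.648 = 1.34, where the truth is 1.00

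**Range of crude ratios with no true effect:**

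| Assumed *yes* shares | f = 0.75 | f = 0.50 | f = 0.25 |
|---|---|---|---|
| 0.60 in every registry | 1.00 | 1.00 | 1.00 |
| UKNHD 0.35, all others 0.60 | 1.03 | 1.06 | 1.11 |
| UKNHD 0.35, all others 0.80 | 1.06 | 1.14 | 1.27 |
| UKNHD 0.35; FranceCoag, HemoNED, CBDR 0.60; WBDR, ATHNdataset 0.80 | 1.10 | 1.24 | 1.48 |
| UKNHD 0.35; FranceCoag, HemoNED, CBDR 0.40; WBDR, ATHNdataset 0.80 | 1.13 | 1.34 | 1.69 |
| UKNHD 0.35; FranceCoag, HemoNED, CBDR, ATHNdataset 0.80; WBDR 0.40 | 0.94 | 0.86 | 0.77 |

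With equal capture (f = 1) the ratio is 1.00 whatever the shares.

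**Placement of FranceCoag.** Table 3 lists it under EUHASS, but 8.4 says it captures AEs and SAEs. With UKNHD at 0.40, all others at 0.70 and f = 0.5, the ratio is 1.08 with FranceCoag as EUHASS type and 1.09 with full capture, so its placement matters little in that scenario.

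**With registry as stratum.** Weight each registry's group rate by its share W_r of pooled person-time. With no effect inside any registry, both groups' standardised rates equal Σ W_r c_r times the common true rate, so the ratio is 1.00 in every row. A Mantel-Haenszel ratio stratified by registry also gives 1.00.

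**Scale against chance.** An assumed 5 SAEs per 100 PY gives 800 × 0.05 = 40 events. Split 24/16, the 95% limits on the ratio lie a factor exp(1.96 × √(1/24 + 1/16)) = 1.88 either side.

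**The case against.** The strongest reply is that bias is not shown, only possible.

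- **Completeness is not prevalence.** A reader might infer from the Low rating in Table 1 that UKNHD has fewer *yes* patients, and so that the contrast is confounded. The rating means only that under 40% of patients have the variable. No *yes* share is given for any registry, unknown status is nowhere coded as *no*, and Table 6 rates UKNHD haemophilia treatments Good. This stands: the documents support *open to confounding*, not *is confounded*.
- **Unknown direction and modest size.** A reader might expect the *yes* rate to be inflated. The table runs to both sides of 1.00, and most entries lie inside the chance factor of 1.88. This stands. So does the absence of any SAE rate in the protocol, which means one cannot claim that SAEs will be numerous enough to read or that this bias would drive the study's conclusion.
- **No comparison is planned.** Section 8.7.1 excludes one. This argues against requiring a ratio, but it does not protect two pooled rates shown under an aim worded as impact.
- **Existing safeguards.** Sensitivity analysis 4 varies the phenotype criteria and eases the entry-route difference, but it leaves AE capture untouched. Region subgroups would separate much of the reporting difference, since the three European national registries use EUHASS or an adaptation. They are conditional on numbers, and multi-country WBDR may fall in more than one region. That *US and Canada* joins two coding systems is minor: ATHNdataset has 15 of 5307 patients. Section 8.9.2 does not discuss AE capture, and none of the four sensitivity analyses varies it.
- **SAP territory.** Section 8.7.1 leaves analytical detail to the SAP, which may add a by-registry table. But the crude pooled estimator and the word *impact* are fixed in the protocol.

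**Conclusion.** The point holds as a cheap improvement. Objective 6 promises an impact, and the stated analysis gives crude *yes*/*no* rates pooled over sources that differ in SAE capture, prophylaxis recording and entry route. The SAE contrast is therefore open to confounding by registry.

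Size and direction cannot be derived from the protocol. With no true effect, the assumed shares (35% in UKNHD, 40% to 80% elsewhere) and capture fractions (25% to 75%) give crude ratios of 0.77 to 1.69. If either the shares or the capture are equal across registries, the ratio is exactly 1.00. The result also rests on starters being spread as in Table 7, while participation still depends on contracting. The point does not bear on the TE results, with about 1.2 events expected, nor in practice on TMA if it is as rare as assumed.

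**What to change.** In section 8.7.2, objective 6:

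1. Tabulate SAE events, person-time and rates by prior prophylaxis within each registry, or within each AE-reporting system where cells are too small.
2. Beside the crude pooled rates, give descriptive rates directly standardised to the pooled distribution of person-time over registries. A registry-stratified ratio is optional, since formal comparison is excluded.
3. Keep patients with unrecorded prophylaxis status outside the *no* group in the rate tables; 8.7.5 already does this in spirit for descriptive tables.
4. Describe the result as incidence by prior prophylaxis, here and in 7.2, instead of as an impact.

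**Cost.** Wording and one more table. Each source already produces its own aggregate under the common data model (8.6), so the counts need no new collection, only that the specification keeps registry and prophylaxis group together. The downside is sparse strata, some with only one group present, and somewhat wider intervals. Standardising removes registry mix from the contrast but does not restore SAEs that a registry never recorded.

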8.7.3. Subgroup Analyses

Subgroup analyses will be carried out for all study objectives (section 7). Analyses specific to each group will be prioritised/de-prioritised following review of patient's numbers for each group. Subgroups of interest include, but are not limited to:

- FVIII prophylaxis use prior to emicizumab treatment initiation (yes/no) in line with secondary objective 6.
- Analysis by geographical regions (Europe; US and Canada; Other).
- Cardiovascular disease including treatment for cardiovascular disease, if feasible (yes/no) prior to emicizumab treatment initiation.
- Age at emicizumab treatment initiation (<50, ≥50 years-old).

All variables that are used to define subgroups will be assessed at the index date which is emicizumab treatment initiation. Further details on subgroups, their categories, and criteria for regrouping of any categories will be described in the SAP.

8.7.4. Sensitivity Analyses

The study will include 4 sensitivity analyses which will be performed on the study objectives. The sensitivity analyses are presented in Table 10 using the HARPER table template for sensitivity analyses (Wang et al., 2023).

Hemlibra—F. Hoffmann-La Roche Ltd Protocol BO44691, Version 2.0

Sensitivity analysis	What is being varied? How?	Why? (What do you expect to learn?)	Strengths of the sensitivity analysis compared to the primary analysis	Limitations of the sensitivity analysis compared to the primary analysis
1	Censoring not done at the end of treatment.	To determine the impact of possible information bias arising from informative censoring and the impact of long-term effects. The approach will be similar to an ITT analysis.	Long-term effects could be masked by censoring at end of treatment. Furthermore, treatment cessation could be linked to AEs.	The causal nature of the relationship between event and end of treatment will be difficult to evaluate if the event occurs long after the end of treatment.
2	All events, not just the first, will be counted for the rate and follow-up continues until end of study period	To determine the impact of all irrespective of 1 st or subsequent outcomes during follow-up.	Full evaluation of the rate of AEs' burden across the follow-up.	All events during study period will measure the all-event rate, wherein all events (incident or subsequent) will be treated as independent. Events will be counted in the numerator for crude event rates and denominator will be the length of follow-up period until end of study period.
3	The maximum length of follow- up will not be set to five-years.	Further determine the long- term safety of emicizumab in the patient population.	Longer follow-up.	Longer follow-up will be correlated with geographical region, due to differences in time of MA, with a likely overrepresentation of patients with a follow-up longer than 5 years outside the EU.

 Table 10. Sensitivity analyses – rationale, strengths and limitations.

Hemlibra—F. Hoffmann-La Roche Ltd Protocol BO44691, Version 2.0

Sensitivity analysis	What is being varied? How?	Why? (What do you expect to learn?)	Strengths of the sensitivity analysis compared to the primary analysis	Limitations of the sensitivity analysis compared to the primary analysis
4	Varying the definition of severe bleeding phenotype using two definitions based on criteria for which all ingoing registries have coverage of both criteria. These definitions will be applied and analysed in two separate sensitivity analyses:	All data sources do not collect all criteria for severe bleeding phenotype (see Table 6). This can result in selection bias wherein patients are included based on the availability of the differing criteria across data sources. By varying the criteria of the severe bleeding phenotype definition in two sensitivity analyses we will test its robustness and gauge potential selection bias.	This will create similar selection criteria across all registries thus reducing potential differential selection across registries.	All three criteria of severe bleeding phenotype are important thus limiting the definition of severe bleeding phenotype might coincidentally introduce other forms of selection bias. As ABR might require both baseline and follow-up visits in the registry, this could result in a smaller sample size in some data sources. Not all registries will be able to fulfil both criteria (see Table 1 for details).

ABR, Annual Bleeding Rate; AEs, Adverse Events; EU, European Union; ITT, Intention to treat; MA, Market Authorisation.

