8.2.4. Follow-up Period

The study will allow for a minimum of 4 years of follow-up after the index date. The follow-up period will be the time period from index date (first emicizumab initiation) until, **Hemlibra—F. Hoffmann-La Roche Ltd** Protocol BO44691, Version 2.0

the end of the study period (anticipated Q4 2030), a maximum of 5 years of follow-up, or censoring.

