8.2.5. Censoring

Patients will be followed until the end of study period or when meeting any of the following censoring criteria, the reason for censoring will be described, whichever occurs first:

- Death
- End of observation, e.g., due to loss to follow-up, emigration, or disenrollment from the registry
- Discontinuation of emicizumab treatment (as defined in the exposure section 8.3.2.2.)

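### Sensitivity analysis 2 treats repeat events in a patient as independent, so its SAE interval is too narrow when events cluster, and its follow-up rule is left ambiguous

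*Protocol*

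**What the plan says.** The primary rate counts first events only. Under section 8.7.2, "The patient time-at-risk will be calculated from index date until the date of an incident event or censoring, whichever occurs first". Section 8.2.4 ends the follow-up period at "the end of the study period (anticipated Q4 2030), a maximum of 5 years of follow-up, or censoring", and section 8.2.5 lists discontinuation of emicizumab among the censoring criteria. Crude rates carry 95% CIs (8.7.2).

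Table 10 in section 8.7.4 sets out four sensitivity analyses on the study objectives, so each covers TE events, SAEs, TMA and serious hypersensitivity.

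- **Analysis 1:** "Censoring not done at the end of treatment".
- **Analysis 2:** "All events, not just the first, will be counted for the rate and follow-up continues until end of study period". Its limitations column adds that this is an all-event rate, "wherein all events (incident or subsequent) will be treated as independent", and that the "denominator will be the length of follow-up period until end of study period".
- **Analysis 3:** removes the 5-year maximum.

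Table 10 names no interval method for analysis 2.

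**The concern.** Two separate matters sit in this one row.

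**The variance.** A patient who has one SAE is usually more likely than average to have another. The total count then varies more than a Poisson count with the same mean, and an interval that treats the events as independent claims more precision than the data hold. The row exists to describe the full burden of adverse events, which is where repeat events carry most weight.

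**The follow-up rule.** If follow-up really runs to the end of the study period, analysis 2 changes three things at once: the event count, censoring at discontinuation and the 5-year cap. A difference from the primary rate would then mix recurrence, off-drug time and later follow-up. The row would not answer its own question, which is what counting later events adds.

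**Working it through.** **1. The plan's own precision figure.** Section 8.5.2 uses 200 patients × 4 years = 800 PY and a TE rate of 0.15 per 100 PY, so 1.2 events are expected. The Clopper-Pearson upper limit is 0.90 per 100 PY with 2 events and 1.09 with 3. The limit therefore stays within 1 per 100 PY when there are at most 2 events, and P(X ≤ 2) = 0.880. This reproduces the stated 88%. It concerns first events only and analysis 2 does not alter it.

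**2. SAE interval under clustering.** The SAE rate and the between-patient variance are assumptions, because the protocol gives neither. Let each patient's rate vary by a gamma factor with mean 1 and variance θ, and let m be the mean number of events per patient (rate × 4 years). The variance of the total count is inflated by 1 + θm, and an honest interval is √(1 + θm) times as wide. The total over 200 patients is negative binomial with size 200/θ, so the coverage of the exact Poisson 95% interval can be calculated directly.

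| SAEs per 100 PY | θ | Expected events | 1 + θm | Width factor | Coverage |
|---|---|---|---|---|---|
| 5 | 1 | 40 | 1.2 | 1.10 | 94% |
| 5 | 2 | 40 | 1.4 | 1.18 | 92% |
| 10 | 1 | 80 | 1.4 | 1.18 | 91% |
| 10 | 2 | 80 | 1.8 | 1.34 | 87% |
| 20 | 1 | 160 | 1.8 | 1.34 | 86% |
| 20 | 2 | 160 | 2.6 | 1.61 | 78% |

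In simulation of the same six settings, a patient-clustered interval on the log scale covers 94 to 95%.

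**3. TE interval.** At 0.15 per 100 PY, m = 0.006. Even θ = 4 gives inflation of only 1 + 4 × 0.006 = 1.024, with coverage of about 99%. If instead 10 to 50% of TE patients had a second event (assumed), inflation is 1.18 to 1.67, yet the exact interval still covers 95 to 98%, because it is conservative at such small counts. A log-scale clustered interval does not exist when there are no events, and P(0 events) = exp(−1.2) = 30%.

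**4. Person-time if the row is read literally.** Assume uniform entry from 23 January 2023 (the EU decision) to the end of 2026, study end at the end of 2030, and no death or loss to follow-up.

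- Potential follow-up runs from 4 to 7.94 years, so the literal mean is (4 + 7.94)/2 = 5.97 years.
- With the 5-year cap and no discontinuation, the mean is (4.5 + 5 × 2.94)/3.94 = 4.87 years.
- With assumed discontinuation of 5% or 10% per year, the primary mean falls to 4.32 or 3.85 years.
- Literal analysis 2 therefore has 23%, 38% or 55% more person-time (5.97 divided by 4.87, 4.32 or 3.85).

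At 10% discontinuation per year, 4.46 of the 5.97 years are on treatment, so 25% of the time is off drug. Suppose recurrence adds 20% to the event count and the off-drug rate is k times the on-drug rate. The ratio to the primary rate is 1.2 × (4.46 + 1.51k)/5.97, which is 1.20 for k = 1, 1.05 for k = 0.5 and 0.97 for k = 0.25. A real recurrence effect of 20% could disappear from view.

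**The case against.** The independence assumption is disclosed: it stands in the limitations column. The interval method is not named and may be set in the SAP. The size of the effect depends on an SAE rate and a variance that the protocol does not give, and at 5 per 100 PY with θ = 1 the loss of coverage is about one percentage point. These points limit the size of the problem but do not remove it. The row states independence as the way events will be handled, and naming a limitation does not widen an interval.

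On follow-up, the row can be read differently. Section 8.2.4 defines the follow-up period as already capped and censored. Where the protocol lifts a rule, it says so openly: analysis 1 for censoring and analysis 3 for the cap. Analysis 2 may mean only that follow-up does not stop at the first event, which any all-event rate requires. The literal reading also cannot hold for every rule, since nobody is followed past death. This stands, and the follow-up point is therefore an ambiguity and not an established design error. Against it, section 8.9.2 describes analysis 1, which does lift censoring at discontinuation, as following patients to the end of the study period. The text does not settle the matter.

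A reader might infer that all intervals in analysis 2 are too narrow, including the one for TE. Step 3 does not support that. A reader might also infer that the analysis cannot be interpreted at all. That goes too far: analyses 1 and 3 show the discontinuation and cap effects separately, and section 8.7.1 makes the study purely descriptive.

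**Conclusion.** The point holds for frequent recurrent events. If SAEs cluster within patients, an independence-based 95% CI covers about 78 to 94% over assumed rates of 5 to 20 per 100 PY and frailty variance of 1 to 2, for 200 patients followed for 4 years. The TE interval is not materially affected at the planned rate, and the primary first-event analysis and its sample-size figures are untouched.

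The follow-up wording needs settling. On the literal reading it adds 23 to 55% person-time under the entry and discontinuation assumptions above. On either reading, no row clearly shows all-event counting under the primary rules.

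**What to change.** **Follow-up.** State in Table 10 that analysis 2 keeps the follow-up and censoring rules of sections 8.2.4 and 8.2.5, except that time at risk does not stop at the first event. Alternatively, report it both ways.

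**Variance.** Replace the independence statement with a patient-clustered (robust) variance for frequent endpoints such as SAEs. With d events and t years per patient, total person-time T and rate r:

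Var(r) = Σ(d − rt)² / T² = (Σd² − 2rΣdt + r²Σt²) / T².

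Keep the exact interval for TE, TMA and hypersensitivity, and for any endpoint with zero or very few events.

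**Data.** Add Σd², Σdt and Σt² to the common data model for the endpoints concerned. They add across registries, so no patient-level transfer is needed. Table 7 shows no patient-level access for WBDR and CBDR, which hold 2987 + 299 = 3286 of the 5307 moderate patients in the considered registries (62%). If these sums are not specified before extraction, the variance cannot be computed from the aggregated data of those two sources.

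**Cost.** One revised table row, one formula, a few extra data-model fields, and wider SAE intervals.
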